## I. INTRODUCTION

Our understanding of diagnosis, treatment and outcomes of coronavirus disease 2019 (COVID-19) is rapidly evolving. First reports from China clearly indicate that older patients with underlying cardiovascular disease and/or cardiac risk factors demonstrate higher mortality rates (1,2). Most recent reports provided novel insights into the incidence of myocardial injury in COVID-19 patients and its association with adverse outcomes (3,4). In both studies, patients with myocardial injury manifested by elevated high-sensitivity troponin I (TnI) levels had significantly higher in-hospital mortality rates compared with those without myocardial injury, (59.6 and 8.9% (3) and 51 vs 4.5 % (4)). Among patients with myocardial injury, higher levels of The were associated with higher mortality rates. While the highest mortality rates were observed in patients with elevated TnI and underlying cardiovascular disease (CVD), mortality rates were also considerable in patients with elevated TnI and without prior CVD. In contrast, patients with known cardiovascular disease without Tnl elevation had more favorable outcomes. Cardiac injury was independently associated with an increased risk of mortality in patients with COVID-19 (4). The arming reports clearly indicate that the data from larger populations from multiple centers are needed to further characterize and better understand the association between myocardial injury and adverse outcomes in COVID-19 patients.

## II. STUDY AIM (What specific question is being addressed?)

The aim of the proposed study is to analyze the incidence, clinical outcomes and predictors of myocardial injury in a large patient population with COVID-19 treated in Mount Sinai Hospital

(MSH) system. In addition, we will explore the association between TnI levels and clinical characteristics, biomarkers, cardiac tests data and treatment approaches to uncover the potential mechanisms responsible for COVID-19 induced myocardial injury.

#### **III. STUDY POPULATION** (What population(s) is being studied?)

By October 2020, there had been 4,695 COVID-19 positive patients treated in the Mount Sinai Hospital (MSH). All consecutive patients admitted to the MSH system from February 2020 to October 2020 with laboratory-confirmed COVID-19 will be included in the retrospective study.

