## **IV. STUDY DESIGN AND PROCEDURES**

Medical history, demographic characteristics, clinical data (symptoms, treatment, complications and outcomes), laboratory findings and cardiac biomarkers on admission and during hospitalization will be collected retrospectively using electronic medical records by trained research personnel and reviewed by physicians. In addition, we will collect available electrocardiography, echocardiography and radiography (chest radiography or computed tomography) data. Patients will be categorized according to the presence or absence of cardiac injury defined as blood levels of high sensitivity troponin (hsTn) above the 99th-percentile upper reference limit. The primary end point will be death; secondary end points will include the rate of pulmonary embolism, acute kidney injury and admission to the intensive care. The study population will be stratified into categories according to the presence and type of myocardial injury according to the Fourth Universal Definition of Myocardial infarction. The cumulative incidence of all-cause mortality will be assessed using the Kaplan-Meier method and compared across the study groups with the log-rank test. Multivariate regression models will be used to determine the independent risk factors for death. Statistical analyses will be performed by an independent statistical center not involved in the data collection

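### The cohort takes in any admission with confirmed COVID-19, whatever the reason for admission or date of infection, so injury from another illness can be credited to COVID-19 in the mechanism and predictor analyses.

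*Combined protocol and SAP*

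**What the plan says.** Section III (Study Population) has a single entry rule: "All consecutive patients admitted to the MSH system from February 2020 to October 2020 with laboratory-confirmed COVID-19 will be included". It lists no exclusions, no criterion on reason for admission, and no window linking the positive test to the admission.

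Section IV (Study Design and Procedures) groups patients by "cardiac injury defined as blood levels of high sensitivity troponin (hsTn) above the 99th-percentile upper reference limit". On timing it says that "laboratory findings and cardiac biomarkers on admission and during hospitalization will be collected retrospectively". It does not require the raised value to follow the infection. The same section says the population will be "stratified into categories according to the presence and type of myocardial injury according to the Fourth Universal Definition of Myocardial infarction". It also provides for collecting history, symptoms, electrocardiography and echocardiography, with physician review.

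Section II (Study Aim) has two parts. The first is descriptive: incidence, outcomes and predictors of injury in patients with COVID-19. The second is exploratory and aims to "uncover the potential mechanisms responsible for COVID-19 induced myocardial injury". Section VI (Outcomes) calls the injury associated with COVID-19, refers to its effect on outcomes after the infection, and plans a model for death due to myocardial injury.

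**The concern.** Two kinds of patient meet the entry rule and the injury definition although COVID-19 may not have caused the injury. One is admitted for an acute coronary event, cardiac surgery or trauma and is found positive on testing. The other is infected during the stay, so that an admission troponin may predate the infection altogether. Both would count as injured COVID-19 patients.

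For a plain description of injury among hospital patients with COVID-19 this does no harm. It matters once the same patients are used to explain how COVID-19 injures the heart, or to say who is at risk of that injury. If such admissions have raised troponin more often than the rest, they are over-represented among the injured. Predictor and mechanism results would then lean towards ordinary cardiac disease. Mortality by injury type could also be affected, though the documents do not allow a direction or size to be given. There is no group without COVID-19 against which to separate the causes.

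**Working it through.** The plan gives no figure to reproduce on this point. The check is a reading of the text followed by an illustration.

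**Text.** Set side by side, Section III fixes neither the reason for admission nor the date of infection, and Section IV fixes neither the cause of the raised hsTn nor its timing relative to infection. No other section supplies these conditions. The regression models in Section IV are for death and name no covariates, so adjustment for reason for admission cannot be presumed. Physician review is planned, but attribution of cause is not among its stated tasks.

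**Illustration.** N = 4,695 is the patient count in Section III. The other inputs are assumptions, not taken from the documents:

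- p, the share admitted for another reason: 10%, with 5% and 20% as alternatives
- r1, the injury rate in that group: 40%
- r0, the injury rate in the rest: 20%

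Formulas:

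- Overall incidence = p·r1 + (1 − p)·r0
- Upper figure, all injuries in the other-reason group as a share of all injured = p·r1 / incidence
- Lower figure, only the excess over the rate in the rest = p·(r1 − r0) / incidence

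At p = 10%:

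- Other-reason patients: 0.10 × 4,695 ≈ 470; injured: 0.40 × 469.5 ≈ 188
- Remaining patients: about 4,225; injured: 0.20 × 4,225.5 ≈ 845
- All injured: 188 + 845 = 1,033; incidence 1,033 / 4,695 = 22%, against 20% in the rest
- Upper figure: 188 / 1,033 = 18%
- Excess: 469.5 × (0.40 − 0.20) ≈ 94; lower figure: 94 / 1,033 = 9%

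| p | Incidence | Lower figure | Upper figure |
|---|---|---|---|
| 5% | 0.02 + 0.19 = 21% | 0.01 / 0.21 = 4.8% | 0.02 / 0.21 = 9.5% |
| 10% | 0.04 + 0.18 = 22% | 0.02 / 0.22 = 9.1% | 0.04 / 0.22 = 18.2% |
| 20% | 0.08 + 0.16 = 24% | 0.04 / 0.24 = 16.7% | 0.08 / 0.24 = 33.3% |

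N cancels from the percentages. It therefore does not matter to them that 4,695 counts patients treated while the entry rule concerns patients admitted.

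The result depends on r1. With r1 = 50%, the upper figures become 0.025 / 0.215 = 12%, 0.05 / 0.23 = 22% and 0.10 / 0.26 = 38%. With r1 equal to r0, the excess is zero.

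**The case against.** The strongest reply is that the main aim is descriptive and an all-comer consecutive cohort suits it. The primary end point is death, and a log-rank comparison by injury group does not need COVID-19 to have caused the injury. The causal wording appears in one exploratory sentence of Section II, and Section VI speaks of association. This stands. A reader might infer that the plan does credit all such injury to COVID-19, or that the incidence and mortality results are invalid. The documents support neither inference. They leave room for misattribution in the mechanism and predictor work.

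The Fourth Universal Definition typing, with physician review, is a real partial safeguard, since it can separate infarction from other injury. But an infarction that prompted admission and one that followed infection can fall in the same type, and the two-group comparison still counts every case.

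A reader might also take 18% as the share of injured patients whose injury is due to another illness. That would require COVID-19 to cause no injury in the other-reason group, although those patients are infected too. The figure is the upper end of a range.

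Finally, restricting every main result to patients admitted for COVID-19 might seem the natural remedy. It could remove patients whose COVID-19 presents as an acute coronary event, and Section VI is expressly interested in the overlap of the epidemic with cardiovascular disease. That objection stands and shapes the fix.

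The entry rule could be read as meaning infection confirmed at admission, but the text states no timing.

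**Conclusion.** The point holds in a limited form. The entry rule and the injury definition together let injury that is unrelated to the infection, or that precedes it, enter analyses framed as being about injury caused by COVID-19. The planned typing reduces this but does not remove it.

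On the assumed 40% and 20% injury rates, roughly 5–10%, 9–18% or 17–33% of injured patients would be affected at other-reason shares of 5%, 10% or 20%. The true share and rates are not in the documents, so these figures show scale only. Hospital-acquired infections with earlier troponin elevation are not quantified separately. The effect on overall incidence is small, two percentage points at the 10% share. What remains is a worthwhile, low-cost improvement to the exploratory and predictor analyses and to the wording of the aim.

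**What to change.** Keep the all-comer cohort for the descriptive incidence and mortality results, and add the following before analysis:

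- **Section IV, data:** abstract the reason for admission, the date of the first positive test and the date of the first raised hsTn.
- **Section III, classification:** label each patient as admitted for COVID-19, admitted for another reason and positive, or first positive after a prespecified number of days in hospital.
- **Section IV, analysis:** repeat the incidence, predictor, mechanism and mortality analyses in patients admitted for COVID-19 as a prespecified sensitivity analysis, and report the other two groups separately.
- **Section IV, timing:** in hospital-acquired cases, do not count hsTn elevations that precede the infection as COVID-19 injury.
- **Section II, wording:** replace the reference to injury induced by COVID-19 with myocardial injury in patients with COVID-19.

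The cost is some extra abstraction within a chart review that is already planned with physician involvement. Section IV does not list these fields by name, so their availability should be confirmed. Classifying reason for admission needs judgement, above all for patients whose COVID-19 presents as a cardiac event, so the rule for them should be written down in advance. No patient is lost from the main cohort. The change reduces misattribution but does not establish cause, since there is still no comparison group without COVID-19.

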## **IV. STUDY DESIGN AND PROCEDURES**

Medical history, demographic characteristics, clinical data (symptoms, treatment, complications and outcomes), laboratory findings and cardiac biomarkers on admission and during hospitalization will be collected retrospectively using electronic medical records by trained research personnel and reviewed by physicians. In addition, we will collect available electrocardiography, echocardiography and radiography (chest radiography or computed tomography) data. Patients will be categorized according to the presence or absence of cardiac injury defined as blood levels of high sensitivity troponin (hsTn) above the 99th-percentile upper reference limit. The primary end point will be death; secondary end points will include the rate of pulmonary embolism, acute kidney injury and admission to the intensive care. The study population will be stratified into categories according to the presence and type of myocardial injury according to the Fourth Universal Definition of Myocardial infarction. The cumulative incidence of all-cause mortality will be assessed using the Kaplan-Meier method and compared across the study groups with the log-rank test. Multivariate regression models will be used to determine the independent risk factors for death. Statistical analyses will be performed by an independent statistical center not involved in the data collection

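### Vital status is not withheld from whoever assigns the type of myocardial injury, so the mortality comparison between injury types is open to outcome-dependent misclassification

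*Combined protocol and SAP*

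**What the plan says.** All the relevant text is in Section IV of the combined protocol and SAP.

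- **Scope of the abstraction.** It covers "clinical data (symptoms, treatment, complications and outcomes), laboratory findings and cardiac biomarkers on admission and during hospitalization". These data "will be collected retrospectively using electronic medical records by trained research personnel and reviewed by physicians". Outcomes therefore pass through the same process as the clinical findings.
- **Presence of injury.** Patients are divided by "cardiac injury defined as blood levels of high sensitivity troponin (hsTn) above the 99th-percentile upper reference limit".
- **Type of injury.** The population is also to be "stratified into categories according to the presence and type of myocardial injury according to the Fourth Universal Definition of Myocardial infarction". No assessor, operational rule, data window, blinding or adjudication is given.
- **Endpoint and comparison.** "The primary end point will be death", and its cumulative incidence is to be "compared across the study groups with the log-rank test".
- **Separation of roles.** The only statement of this kind is "Statistical analyses will be performed by an independent statistical center not involved in the data collection".

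Section III sets the cohort as admissions from February to October 2020, studied retrospectively.

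**The concern.** Death is an objective endpoint, so the step that needs protection is the grouping. Presence of injury is fixed by a laboratory threshold. Type is not, because one cut-off cannot separate several types of injury. Something more from the record has to be used, and the plan lists symptoms, complications, electrocardiography, echocardiography and radiography without saying how they combine.

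The study is retrospective, so in-hospital deaths will generally already be in the record when it is opened. A physician who types an uncertain case from that record can see how it ended. If this sways the label even modestly, misclassification depends on the outcome, and mortality differences between types can be created, enlarged or hidden. The independent statistical center does not cure this: being outside data collection does not blind whoever assigns type, and a label influenced by outcome looks like any other in the dataset. If type also enters the prediction model or the mechanistic work in Section VI, the error carries into those.

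**Working it through.** The plan gives no sample size, power or effect size for this comparison, so there is no figure to reproduce. The check has two parts.

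**1. Reading the text.**

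| Step | What Section IV states | Is vital status hidden? |
|---|---|---|
| Data collection and physician review | One process, outcomes included | No |
| Presence of injury | hsTn cut-off | Not stated, but a laboratory value leaves little room for influence |
| Type of injury | Fourth Universal Definition categories, no procedure | Not stated |
| Analysis | Independent center, outside data collection | Does not bear on how type is assigned |

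Type is the one step that is both unprotected and not fixed by a stated numerical rule.

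**2. Illustration of size, under assumptions.**

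From the documents: 4,695 patients (Section III). Mortality with injury was 59.6% and 51% in the two cited reports (Section I); 50% is used here as a round value.

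Assumed: 30% injured, 0.30 × 4,695 ≈ 1,408; two types, A and B, of equal size (704 each) with the same true mortality; a share *a* of cases ambiguous; a fraction *s* of ambiguous deaths and 1 − *s* of ambiguous survivors labelled A.

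- Share of deaths labelled A: (1 − a)/2 + a·s
- Share of survivors labelled A: (1 − a)/2 + a·(1 − s)

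At 50% mortality, deaths and survivors are equal in number and the labelled groups keep equal size. Observed mortality is then the first expression in A and the second in B, and the false gap is a(2s − 1). The standard error is √(0.25 × 2/704) = 0.0267. The two-proportion z stands in for the log-rank statistic.

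| Ambiguous share a | Split s | Observed A vs B | Gap | z |
|---|---|---|---|---|
| 20% | 75/25 | 0.40 + 0.15 = 55% vs 0.40 + 0.05 = 45% | 10 points | 3.75 |
| 20% | 60/40 | 0.40 + 0.12 = 52% vs 0.40 + 0.08 = 48% | 4 points | 1.5 |
| 10% | 75/25 | 0.45 + 0.075 = 52.5% vs 0.45 + 0.025 = 47.5% | 5 points | 1.9 |
| 10% | 60/40 | 0.45 + 0.06 = 51% vs 0.45 + 0.04 = 49% | 2 points | 0.75 |

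The true gap is zero in every row. Only the first row passes 1.96, but an expected z of 1.5 still carries a chance of about P(Z > 1.96 − 1.5) = P(Z > 0.46) ≈ 32% of a significant result in that direction, against a nominal 2.5%. Exchanging A and B reverses the sign, so the table says nothing about direction.

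The injured share matters too. With 500 injured patients the standard error is √(0.25 × 2/250) = 0.0447, and z runs from 0.02/0.0447 ≈ 0.45 to 0.10/0.0447 ≈ 2.2.

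**Cross-check with a different mechanism.** Take two equal types with 51% mortality and move a share *m* of one type's deaths to the other. The odds ratio becomes (1 + m)/(1 − m). For m = 10% it is 1.1/0.9 = 1.22, with apparent mortality 0.459/0.949 = 48.4% vs 0.561/1.051 = 53.4%. The chance of a false finding in that direction is 20%, 35% and 49% for 500, 1,000 and 1,500 injured patients. For m = 5% it is 8%, 12% and 16%.

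**The case against.** The strongest reply is that the plan never describes how type is assigned. The sentence on electronic records concerns data collection, and the stratification sentence is in the passive. Type could be derived from abstracted fields by a fixed rule, or at the analysis stage, with little room for influence. This stands as a limit: assignment from the chart is an inference. It is the natural one, because the electronic record is the only data source described and physician review the only clinical step.

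A reader might also infer several stronger claims that the documents do not support:

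- *That the groups are fixed before the statistical center acts.* Section IV does not say when, or by whom, they are fixed.
- *That the primary comparison is compromised.* Death is the primary endpoint, but no comparison is named as primary. Section IV gives two groupings, the log-rank sentence refers only to the study groups, and the aim in Section II does not mention type. Injured versus not injured rests on the laboratory cut-off.
- *That uncertain deaths will drift to a graver type.* The plan does not rank the types, so direction is unknown.
- *That the bias has occurred, or is large.* The text shows only that nothing prevents it. Most of the inputs to the illustration are assumed, and three of its four combinations fall below 1.96.

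A further objection is that hiding the later course could itself bias the typing. Only available electrocardiograms and echocardiograms are collected, and patients who die early may have fewer, so an indeterminate category could be enriched for early deaths. That is fair, and the fix has to deal with it.

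**Conclusion.** The concern holds in a limited form. Section IV handles outcomes together with the clinical data and does not keep vital status from whoever assigns type. If type is assigned from that record, the between-type mortality comparison is open to outcome-dependent misclassification of unknown size and direction. The comparison of injured with not-injured patients is largely unaffected.

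This is more than a missing detail, because a better order of work is available within the existing two-step process of abstraction and physician review. The figures (false gaps of 2 to 10 points, z about 0.75 to 3.75) show only that modest influence on a minority of cases could matter. They rest on an assumed 30% injured, two equal types, 50% mortality, and the stated ambiguous shares and splits, and they do not estimate what will happen in this study.

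**What to change.** Amend Section IV to state that:

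1. The reviewing physicians assign type from abstracted fields limited to a pre-defined window around the index troponin elevation: history, symptoms, serial troponins, and available ECG and imaging. The plan defines no such window now, so it must be written down, with the rules for each category.
2. Discharge status, death and later notes are withheld at that step, and the category is locked before outcome fields are merged.
3. Cases that cannot be typed form a separate indeterminate category, reported with its number and mortality.
4. A sensitivity analysis reallocates the indeterminate cases, for example all to each type in turn and then in proportion to the typed cases, because early deaths may be over-represented among them.

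If type is instead to be derived by a fixed algorithm, stating the algorithm and its input fields would largely meet the point. If charts have already been reviewed, typing can be done by physicians who have not seen those charts.

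The cost is some extract preparation and some indeterminate cases; no new patients, data or staff are needed. One limit remains: a death inside the window may still be guessed from a short troponin series, which is a further reason to report the sensitivity analysis.

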## VI. OUTCOMES (What is the anticipated actionable outcome?)

The study will provide novel insights into the incidence and consequences of COVID-19 associated myocardial injury in US population and its impact in early and late outcomes after the infection. We plan to develop a statistical model to predict the risks for myocardial injury induced death in COVID-19 patients and identify responses to different treatment strategies. This information will be pivotal for other centers who have yet had the surge of COVID cases. We

plan on fast track publication. Furthermore, electrocardiography, echocardiography and radiology data analyses will be used to uncover the potential mechanisms responsible for the link between myocardial injury and mortality. The findings will provide invaluable insights into the clinical outcomes and mechanisms underlying the collision between the acute COVID-19 epidemic and ongoing epidemic of cardiovascular disease.

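### Does the 99th-percentile troponin split throw away the mortality gradient with troponin level?

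*Combined protocol and SAP*

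**What the plan says.** Section IV (Study Design and Procedures) classifies patients by presence or absence of cardiac injury, "defined as blood levels of high sensitivity troponin (hsTn) above the 99th-percentile upper reference limit". The population is also "stratified into categories according to the presence and type of myocardial injury", following the Fourth Universal Definition. All-cause mortality is then compared across the groups by Kaplan-Meier and log-rank.

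Two models for death follow. Section IV states that "Multivariate regression models will be used to determine the independent risk factors for death". Section VI (Outcomes) adds: "We plan to develop a statistical model to predict the risks for myocardial injury induced death in COVID-19 patients". Neither statement lists covariates or gives a form for troponin.

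Level appears in three other places. The Introduction says "Among patients with myocardial injury, higher levels of The were associated with higher mortality rates", where the odd word is evidently a slip for TnI. Section II (Study Aim) plans to "explore the association between TnI levels and clinical characteristics, biomarkers, cardiac tests data and treatment approaches". Section IV says that "cardiac biomarkers on admission and during hospitalization will be collected retrospectively".

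**The concern.** The only troponin exposure written down for mortality is a threshold, and injury type is a category rather than a level. The plan's own background says level matters above the threshold, and the aim that uses levels does not list death among the associations.

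If the threshold were the only troponin term in the models, two things would go wrong. The prediction model would give a patient just over the limit the same troponin contribution as one far above it. In the regression, any factor correlated with level would absorb part of the unmodelled gradient and could be reported as an independent risk factor when it is not.

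**Working it through.** **What the text commits to.** The cut appears in the sentence that forms groups. Incidence, Kaplan-Meier and log-rank need groups, so the cut belongs there. The regression sentence and the prediction-model sentence do not mention it. Level is neither promised nor excluded for either model.

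**Is the group comparison harmed?** The plan gives no power figure to reproduce. Take 4,695 patients (Section III), the Introduction's mortality pairs, and an assumed injured share of 10%, giving 469.5 injured and 4,225.5 not injured.

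- 59.6% vs 8.9%: difference 0.507; SE = √(0.596×0.404/469.5 + 0.089×0.911/4225.5) = 0.023; z ≈ 22.
- 51% vs 4.5%: difference 0.465; SE = √(0.51×0.49/469.5 + 0.045×0.955/4225.5) = 0.023; z ≈ 20.

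Power is about 100%, and the same holds at shares of 20% and 30%.

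**What would be lost if only the binary term were modelled?** The documents give no injured share p, troponin distribution, gradient or covariate correlation r, so these are assumed. Log-troponin is normal and p is 10%, 20%, 36% or 50%. Risk is flat below the limit at 8.9% (or 4.5%). Above it, logit(risk) = a + ln(OR)·z, where z is log-troponin standardised among the injured, a is set so that mean risk is 59.6% (or 51%), and OR is 1.5 or 2.0 per SD.

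True risk at the 10th and 90th troponin percentiles among the injured, over all four values of p:

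| Mean risk in injured | OR 1.5 | OR 2.0 |
|---|---|---|
| 59.6% | 49-50% to 73% | 42-44% to 81% |
| 51% | 40-41% to 65% | 33-35% to 74% |

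A binary term assigns everyone the mean. That is a real loss of discrimination, if the term is used alone.

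**False association for a null factor.** A standard normal factor with no effect on death, correlated r with log-troponin, was entered in a logistic model beside binary injury in 1,000,000 simulated patients. Its standard error was then scaled to 4,695 patients. Ranges cover both mortality pairs and both ORs.

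| p | r = 0.3: false OR (expected z) | r = 0.5: false OR (expected z) |
|---|---|---|
| 10% | 1.01-1.03 (0.3-0.5) | 1.02-1.06 (0.4-0.9) |
| 20% | 1.02-1.06 (0.5-1.0) | 1.04-1.11 (0.9-1.8) |
| 36% | 1.04-1.08 (1.0-1.8) | 1.08-1.16 (1.8-3.2) |
| 50% | 1.06-1.11 (1.4-2.6) | 1.11-1.21 (2.5-4.5) |

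At r = 0.3, z passes 2 only at p = 50% with OR 2.0. At r = 0.5 it stays below 2 for p of 10-20% and passes 2 in most settings at 36% and in all at 50%.

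**A harsher assumption.** If risk were log-linear over the whole troponin range, the split would keep φ(c)²/[p(1−p)] of the information, where c is the normal quantile at 1−p: 0.34, 0.49, 0.61 and 0.64 at the four values of p. The Introduction reports the gradient only among injured patients, so the documents do not support applying these figures here.

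**The case for a change.** The best case for a change is that silence is itself a weakness. The data are retrospective, so an unstated coding of troponin can be chosen after the results are seen. The aim that uses levels does not name death. The prediction model is a stated deliverable intended for use at other centers. Both admission and in-hospital values are collected, and a peak value depends on how long a patient survives and how often troponin is drawn. A few sentences would settle all this and would need no new data.

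Much of that is true. The form is unstated, the risk range within the injured group is wide under plausible gradients, and with many injured patients and a strong correlation the false association would be detectable. But it describes models whose whole covariate list is still to be written; troponin's form is one item among many. The list in the Study Aim concerns mechanism and is not a covariate list for death, so its omission of death is weak evidence that level would be left out. The choice of measurement and its scaling are separate questions from the threshold. The simulation also leaves out injury type, which the plan does use for stratification. If type tracks level, the false association would be smaller than shown.

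**Conclusion.** This is a gap that analysts can fill sensibly, not a wrong choice. The threshold does the job it is given, forming groups for an unadjusted comparison that has ample power. No text imposes it on the regression or the prediction model. The investigators cite the gradient, plan to analyse levels and collect the values, and an independent statistical center does the analysis. Entering troponin level in the models is consistent with the plan as it stands.

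The potential cost depends on a step the plan does not take. If it were taken, patients assigned 59.6% would truly range from about 42-50% to 73-81% between the 10th and 90th troponin percentiles. Spurious odds ratios for a null factor would be 1.01 to 1.21 per SD, with expected z below 2 throughout at injured shares of 10-20%. These figures rest on the assumed injured share, log-normal troponin, OR of 1.5 to 2.0 per SD and correlation of 0.3 to 0.5, and on 4,695 patients being analysed. The conclusion that no change is needed rests on the text and not on these figures.

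### The secondary end points have no timing rule, so embolism, kidney injury or ICU admission already present when hsTn is raised is not excluded and could be reported as an outcome of injury

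*Combined protocol and SAP*

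**What the plan says.** Section II sets out to "analyze the incidence, clinical outcomes and predictors of myocardial injury". It therefore asks both what follows injury and what precedes it.

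Section III admits everyone: "All consecutive patients admitted to the MSH system from February 2020 to October 2020 with laboratory-confirmed COVID-19 will be included". A patient who arrives with an embolism, with kidney injury or in need of intensive care is not excluded.

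Section IV defines the groups by an upper reference limit: "Patients will be categorized according to the presence or absence of cardiac injury defined as blood levels of high sensitivity troponin (hsTn) above the 99th-percentile". It does not say which sample decides the group. On measurement times it says that "laboratory findings and cardiac biomarkers on admission and during hospitalization will be collected retrospectively".

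Section IV then names death as the primary end point and adds that "secondary end points will include the rate of pulmonary embolism, acute kidney injury and admission to the intensive care". Kaplan-Meier and log-rank methods are given for all-cause mortality, and regression for death. The secondary end points have no method, time origin, window or onset rule.

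Section VI says that the study will inform on "incidence and consequences of COVID-19 associated myocardial injury in US population and its impact in early and late outcomes after the infection".

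**The concern.** Death cannot come before the troponin sample. The three secondary events can. A patient may arrive with kidney injury and a raised hsTn on the same blood draw, or may be admitted to the ICU and have a first raised hsTn two days later. Under a plain rate, each patient contributes a secondary event to the injured group, although nothing has been shown to follow the injury.

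Two things are at stake. First, the aim separates outcomes from predictors, and without a timing rule the same kidney injury could be reported as either. Second, if events present early tend to accompany a raised hsTn, a crude comparison between groups could show an excess even where injury leads to no new events. Fixing the start of the mortality clock would not settle this, because events already present at that time would still be in the rate.

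**Working it through.** **The text.** The plan states no rate, sample size or power figure for these end points, so there is no figure of its own to reproduce. The check on the wording has three steps.

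1. Exposure: hsTn above the limit, sample unspecified, biomarkers taken on admission and during the stay (section IV). The exposure can be met at any time in hospital.
2. End points: plain rates, with no date condition (section IV). Eligibility removes no one who already has the event (section III).
3. Hence an event before or at the raised hsTn is not excluded. That it cannot be a consequence of the injury is a matter of chronology and needs no outside source.

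**Illustration (all inputs assumed).** Kidney injury is used as the example.

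- p = share with kidney injury at arrival: 0.15
- q1 = probability of raised hsTn if kidney injury is present at arrival: 0.25 to 0.60
- q0 = the same probability for everyone else: 0.25
- L = later new kidney injury among those free of it, regardless of hsTn: 0.15, so the true ratio for new events is 1.0

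Share with kidney injury at arrival among the injured: a1 = p·q1 / [p·q1 + (1−p)·q0].
Share among the uninjured: a0 = p(1−q1) / [p(1−q1) + (1−p)(1−q0)].
Crude rate in each group: R = a + (1−a)·L.

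For q1 = 0.60:

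- Injured: a1 = 0.0900 / (0.0900 + 0.2125) = 0.2975; R = 0.2975 + 0.7025 × 0.15 = 0.403.
- Uninjured: a0 = 0.0600 / (0.0600 + 0.6375) = 0.086; R = 0.086 + 0.914 × 0.15 = 0.223.
- Ratio: 0.403 / 0.223 = 1.81.

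Varying q1, with the other inputs unchanged:

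| q1 vs q0 | Injured | Uninjured | Crude ratio | Ratio, new events only |
|---|---|---|---|---|
| 25% vs 25% | 27.8% | 27.8% | 1.00 | 1.00 |
| 30% vs 25% | 29.9% | 27.0% | 1.11 | 1.00 |
| 40% vs 25% | 33.7% | 25.5% | 1.32 | 1.00 |
| 60% vs 25% | 40.3% | 22.3% | 1.81 | 1.00 |

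Varying p, with q1 = 60%: p = 5% gives 24.5% / 17.3% = 1.42, and p = 25% gives 52.8% / 27.8% = 1.90.

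The first row shows what drives the result. Early events distort the ratio only if they are associated with raised hsTn. Without that association the rates still mix old and new events, but the ratio is not biased.

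**The case against.** The strongest reply is that silence is not a rule. The plan nowhere says that earlier events will be counted, and section IV also speaks of complications, which may mean events arising in hospital. This stands: the defect is an omission. It does not remove the point, because a plain rate gives the statistical center no basis for leaving earlier events out.

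A reader might infer that section VI presents embolism, kidney injury and ICU admission as consequences of injury. It does not name them. Its sentence concerns injury and outcomes after the infection, and the rest of the section turns to death. The firmer anchor is the phrase on clinical outcomes in section II, and that section also has associational aims.

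A reader might also infer that the results will show a false excess, with cause and effect reversed. The documents do not support that. They specify no between-group comparison for these end points, although one is likely. They do not say that embolism or kidney failure raises troponin, or that ICU patients are sampled more often. What they support is unclear temporal order, with inflation possible.

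The study plans to stratify by presence and type of injury under the Fourth Universal Definition. That classifies the injury; as used in section IV it sets no timing rule for the end points.

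Finally, the remedy needs an index sample that the plan does not define and dates that the record may hold only as diagnosis dates. Both limits are real and are taken up in the fix.

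**Conclusion.** The concern holds as an unspecified timing rule. As written, the plan does not exclude secondary events that were present before or at the raised hsTn, and these could be reported as clinical outcomes of injury. Confidence in that omission is high.

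The size is not known. In the kidney-injury illustration the crude ratio runs from 1.0 to 1.9 when the true ratio for new events is 1.0. It depends mainly on how strongly early events go together with raised hsTn, and on how common they are. These are assumed inputs and not bounds, and no corresponding calculation is shown for embolism or ICU admission.

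The change should be made, because the undated rate can give a wrong answer to the aim of separating outcomes from predictors. Its weight is limited: only secondary end points of a retrospective study are touched.

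**What to change.** In section IV:

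1. Name one index hsTn sample, defined the same way for all patients (for example the first in-hospital sample), and assign injury groups from it for this analysis.
2. Count each secondary end point as a first event documented after that sample, among patients free of the event at that time.
3. Tabulate events documented at or before the sample by injury group, as baseline characteristics.
4. Because records may give the date of diagnosis rather than of onset, add a sensitivity analysis that treats events diagnosed shortly after the index sample (for example within 24 hours) as already present.
5. If overall in-hospital rates are also shown, describe them as associations.

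In sections II and VI, where these end points are meant, keep the words outcomes and consequences for after-index events.

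The cost is fewer counted events, denominators that differ by end point (patients who go directly to the ICU leave the ICU end point), and some abstraction of dates. Diagnosis dates will leave some misclassification, which the sensitivity analysis gauges but does not remove.
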